### *Clinical Measurements*

For the assessment of the periodontal and marginal health status the following variables will be measured on mid buccal surface of the treated teeth by the calibrated blinded examiner, using a calibrated North Carolina University probe. The measures will be rounded to the nearest 0.5mm:

1. Distance between CEJ and the free gingival margin (*Rec depth*)
2. Distance between incisal margin to the free gingival margin (*IM-GM*)
3. *Recession width (Rec width)*, represented by the horizontal measurement of gingival recession at the CEJ level
4. *Bleeding on Probing (BOP)*, recording the presence/absence of bleeding after probing (Ainamo & Bay 1975)

5. *Plaque Index (PI)*, recording the presence/absence of plaque on tooth surface (Ainamo & Bay 1975)
6. *Probing Pocket Depth (PD)*, measured using a periodontal probe between GM and the end of the gingival sulcus
7. *Clinical Attachment Levels (CAL)*, calculated as PD+Rec depth
8. *Keratinized tissue (KTw) width*, assessed with the visual and functional method by means a probe as a distance between GM and mucogingival junction (MGJ)
9. *Keratinized tissue (KT thick) thickness*, measured by the use of a needle pierced through the center of a circular-shaped silicon marker of 3 mm in diameter. The edge of the marker (k-file nr. 10) will be positioned at the soft tissue margin providing a distance from the margin of 1.5 mm. The distance between the tip of the needle and the silicon marker will be assessed by the use of a magnifying glass and a Dentsply Maillefer silicon stops AO197 will be used. In addition, a digital calliper C041 0-150 mm (Kennon Instruments) with a sensibility of 0.01 mm will be used (da Silva et al. 2004; Santamaria et al. 2008)
10. Duration of the surgery (in minutes), where the chronometer started from the first incision and stopped at last suture.

The periodontal indexes will be measured before the surgery (baseline) and at the follow-up visits, 3, 6 and 12 month after the surgery.

Standardized photos will be taken at baseline, after flap elevation, after material application, after suturing, and at 7 and 14 days, 1, 3, 6 and 12 months post-op. All pictures will be taken always frontal and in profile.

#### *Patient Reported Outcomes*

A first questionnaire will be given to the patients to assess the baseline in problems with aesthetics, discomfort while brushing teeth, and hypersensitivity (whereas zero is no problem and 10 is major problems). Afterwards, patients will be instructed to use a diary for the first 7 days after the surgery to record patient reported experience measures (PREMs). In the diary patients had to record post-surgery sequelae, pain and discomfort, chewing function, interference with daily activities, use of medications more than the prescription. This questionnaire will be then collected at 7 days after surgery.

At 6 and 12 months, other two questionnaires will be administered in order to record data about discomfort, chewing function, tooth cleaning procedures, dental hypersensitivity and esthetic outcome.

### *Calibration session*

Only 1 calibrated examiner (LG) took all the measurements. For *recession depth* and *incisal margin-gingival margin* measurements, an intra-rater agreement study was performed for the examiners. A set of 20 recessions were evaluated twice with a two-hour interval between the measurements. The examiner was considered reliable if the intraclass coefficient of correlation was greater than 0.70.

### **Sample Size**

The following 2 hypothesis were considered: H0, where there is no difference in mean recession reduction between CAF+XCM and CAF alone; H1, where there is a difference in mean recession reduction between CAF+CM and CAF alone.

The following variables were used in order to calculate the sample size:

- Endpoint: Normal. Difference in reduction in gingival recession (root coverage) between baseline and 1 year
- Clinical important difference (Effect size d): set at 1 mm
- Assessing variability: From a previous study (Woodyard et al. 2004) in an envelope type of CAF for multiple recessions the standard deviation of recession reduction was 0.93 mm.
- Mean number of treated teeth per patient: from a previous study (Woodyard et al. 2004) it was 2.92
- Intraclass correlation coefficient (ICC) of the cluster sites (recessions nested into patient): from a previous study (Woodyard et al. 2004) it was 0.35
- Allocation ratio: 1:1
- Type I error:  $\alpha = 0.05$
- Type II error:  $\beta = 0.10$ , corresponding to a Power of 90%
- Accounting for drop-out: Anticipation of 10% of patient drop-out.

Based on this consideration and applying a formula for cluster design to detect a difference between treatments of 1 mm in recession reduction (standard deviation of 0.93 mm - Woodyard et al. 2004) with a two- side 5% significance level, a power of 90%, a mean number of treated teeth per patient

of 2.92, an intraclass correlation coefficient of 0.35, a sample size of 12 patients per treatment will be necessary.

### **Randomization and Allocation Concealment**

The recession sites will be randomized to one of the two groups: CAF + CM (test group) and CAF alone (control) at a ratio of 1:1. Randomization code will be computer generated by a researcher not involved in the clinical evaluation (MN). A blocked randomization will be used: the 24 patients will be divided in 12 patients per treatment. For designation of the treatment to each patient, the center will receive 24 sequentially numbered and sealed envelopes containing the information on the applicable surgery. The envelope will be opened by the investigator only after flap elevation.

### **Blinding**

Whereas the surgeon will be aware of the allocation arm, patients and the outcome assessors will be kept blinded to the allocation.

### **Data analysis**

Descriptive statistics will be performed using a mean and standard deviation for quantitative data and frequency and percentage for qualitative data. All unintentional side effects in each group will be reported. For quantitative variables mixed models will be performed with the treatment (CAF versus CAF+CM) as a fixed explicative variable and patient as a random variable. Baseline value will be used as a covariate. Interaction terms between treatment and the covariate will be used only if significant.

Complete root coverage will be analysed with a multilevel logistical model at two level (patient and tooth). For the patient-reported outcomes and experience measures t-tests will be applied. Estimates for the treatment effect, standard errors, p-values and 95% confidence intervals are provided. The statistical software will be MLwiN 2.21 Centre for Multilevel Modelling, University of Bristol.

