#### *Inclusion Criteria*

1. The patient (male or female) must be 18 years or older
2. Presence of gingival recessions in the upper jaw, involving teeth from central incisor to first molar
3. Gingival recessions on at least 2 adjacent teeth with a minimal depth of 2mm and detectable cemento-enamel junction (CEJ) (abrasion step <1mm)
4. The patient is able to comply with the study-related procedures such as exercising good oral hygiene and attending all follow-up procedures
5. Full Mouth Plaque (FMPS) and Bleeding (FMBS) Score <20%
6. The patient is able to fully understand the nature of the proposed surgery and is able to provide a signed informed consent

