## **Outcomes**

The objective of this RCT is to compare the coronally advanced flaps with a xenogeneic collagen matrix (test group) versus coronally advanced flaps alone (control group) in the treatment of multiple recession defects. In order to establish a superiority effect of the collagen matrix, the following endpoints will be considered:

*Primary Endpoint:* Mean recession reduction after 6 and 12 months post treatment

*Secondary Endpoints:*

- 1) Percentage of complete root coverage after 6 and 12 month
- 2) Thickness of soft tissue over the root after 6 and 12 month
- 3) Recession width after 6 and 12 month.
- 4) Keratinized Tissue (KT) width
- 5) Patients satisfaction

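### No covariate is named for the complete root coverage model; prespecifying the tooth's baseline recession depth would remove sensitivity to chance imbalance at almost no cost

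*Combined protocol and SAP*

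**What the plan says.** The Outcomes section lists CRC first among the secondary endpoints: "Percentage of complete root coverage after 6 and 12 month". The Data analysis section treats the two kinds of outcome separately.

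- **Quantitative outcomes:** "For quantitative variables mixed models will be performed with the treatment (CAF versus CAF+CM) as a fixed explicative variable and patient as a random variable". The same paragraph adds: "Baseline value will be used as a covariate".
- **CRC:** the next paragraph opens with "Complete root coverage will be analysed with a multilevel logistical model at two level (patient and tooth". It gives the model type and the two levels, and no covariate.

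Under Clinical Measurements, Rec depth is defined for the treated teeth as "Distance between CEJ and the free gingival margin", and the timing is: "The periodontal indexes will be measured before the surgery (baseline) and at the follow-up visits, 3, 6 and 12 month after the surgery". Entry requires: "Gingival recessions on at least 2 adjacent teeth with a minimal depth of 2mm", with no upper limit on depth. On allocation, the plan says: "A blocked randomization will be used: the 24 patients will be divided in 12 patients per treatment". No stratification by depth is stated.

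**The concern.** Every treated tooth starts with a recession, so CRC has no informative baseline value of its own. Even a reader who believes the baseline rule was meant to extend to CRC cannot tell which variable to enter. The natural choice is the tooth's baseline Rec depth: if CRC means a Rec depth of zero at the visit (the plan gives no explicit definition), a deeper defect has further to go. That value is already collected.

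With 12 patients per arm and nothing in the design to balance depth, the arms will differ somewhat in mean depth by chance. The primary analysis adjusts for baseline. The CRC model, read literally, does not, so the two could diverge partly because of imbalance. What is at stake is the precision of the CRC comparison and its sensitivity to the luck of the allocation.

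**Working it through.** **The plan's own figure.** The plan states no sample size or power for CRC. Its 12 patients per arm, for recession reduction, reproduces from the Sample Size inputs (difference 1 mm, SD 0.93 mm, two-sided 5%, power 90%, 2.92 teeth per patient, ICC 0.35, 10% drop-out):

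- teeth per arm: 2 × (0.93 × (1.960 + 1.282) / 1)² = 18.18
- design effect: 1 + (2.92 − 1) × 0.35 = 1.672
- patients per arm: 18.18 × 1.672 / 2.92 = 10.41
- with drop-out: 10.41 / 0.90 = 11.56, so 12

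**Assumptions for CRC.** The documents give no depth SD, no relation between depth and CRC, and no CRC rates. I assume a depth SD of 0.8 to 0.9 mm and a fall of 0, 0.5, 1.0 or 1.5 logits in CRC per mm of depth. The ICC of 0.35 is the plan's figure for recession reduction, and using it for baseline depth is a borrowing. I take the patient as the unit of allocation, since the envelopes are per patient.

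**Size of the chance imbalance.** The number of teeth per arm is 2.92 × 12 = 35.04. The SD of the between-arm difference in mean depth is sqrt(2 × SD² × 1.672 / 35.04):

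- SD 0.8 mm: sqrt(2 × 0.64 × 1.672 / 35.04) = 0.247 mm
- SD 0.9 mm: sqrt(2 × 0.81 × 1.672 / 35.04) = 0.278 mm

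At 1 logit per mm, an imbalance of 0.25 mm multiplies the unadjusted odds ratio by about exp(0.25) = 1.28, and one of 0.5 mm by about exp(0.5) = 1.65. The second case is 0.5/0.278 = 1.8 to 0.5/0.247 = 2.0 SDs, so on a normal approximation it arises in only about 4 to 7% of trials, both directions together.

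**Simulation.** There were 2,500 trials per scenario, each with 12 patients per arm and 2 to 4 teeth per patient (mean 2.92). Depth had mean 3 mm and SD 0.9 mm, rounded to 0.5 mm with a floor of 2 mm. The patient intercept SD was 1.3, and the conditional treatment log odds ratio was 1.8 (about 50% against 76 to 80% of teeth covered). Each trial was fitted with a random-intercept logistic model (15-point quadrature, very weak penalty on the coefficients) and tested by likelihood ratio at 5%, with and without depth. The simulated imbalance SD was 0.25 mm.

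| Logits lost per mm | Power without depth | Power with depth | Gain (points) | Null rejection without / with |
|---|---|---|---|---|
| 0 | 60.2% | 60.2% | 0 | 5.2% / 5.5% |
| 0.5 | 58.8% | 60.3% | 1.5 | 6.1% / 6.0% |
| 1.0 | 54.2% | 58.8% | 4.6 | 5.8% / 5.5% |
| 1.5 | 47.1% | 55.0% | 7.9 | 6.0% / 6.5% |

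Simulation error is about 1 point on each overall power figure and larger in the subgroups below.

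- At slopes 0.5, 1.0 and 1.5, the unadjusted log odds ratio falls by about 0.6, 1.0 and 1.4 per mm by which the test arm is deeper. After adjustment the dependence is near zero (−0.08 to −0.01).
- The crude CRC difference moves by about 9–10, 17–18 and 23–25 percentage points per mm, so a 1-SD imbalance (0.25 mm) is worth about 2, 4 and 6 points.
- At slope 1.0, unadjusted power is 73% when the test arm is shallower by more than 1 SD and 35% when it is deeper by more than 1 SD. Adjusted power is 58% and 56%.
- Also at slope 1.0, among trials with imbalance over 1 SD in either direction, null rejection is 8.0% unadjusted and 5.6% adjusted.

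A second simulation with other settings (600 trials per scenario, log odds ratio 2.0, patient variance 1.77) gave power of 66 against 67%, 64 against 67% and 58 against 66% at slopes 0.5, 1.0 and 1.5. The gains are of the same order. The correlation of the unadjusted estimate with the imbalance was about −0.14, −0.27 and −0.37.

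**The case against.** The strongest reply is that the CRC sentence is shorthand. It does not name the treatment term either, yet treatment must be in the model, so silence about depth does not show that depth was ruled out. That stands. A reader might infer that the plan deliberately excludes adjustment, but the text supports only that the covariates are unspecified.

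A second reply is that an unadjusted randomised comparison of a binary secondary endpoint is legitimate. That also stands. A reader might infer bias or an excess of false positives, but allocation is random and the overall null rejection is about 5 to 6.5% under either model. The 8.0% figure applies only to the subset of trials with a large imbalance.

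A third reply is that the effect is modest and rests on assumption. Squaring the correlations above gives 2%, 7% and 14%, so at least 86% of the variance of the estimate is unrelated to depth imbalance. Only the steepest assumed slope gives a sizeable gain in power, and at slope 0 there is none. This limits the weight of the point but does not remove it, since adjustment cost no power even at slope 0.

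A fourth reply is sparseness. At 50% and 80% coverage on about 35 teeth per arm, some 17.5 + 7 = 24.5 teeth remain uncovered, or about 22 after 10% drop-out. The caution is fair. In the 2,500-trial runs, treatment estimates beyond 8 on the log odds scale occurred in at most 0.5% of trials, though those fits carried a weak penalty.

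Last, a reader might infer that an odds ratio contradicts an endpoint stated as a percentage. It does not: the plan already provides for descriptive percentages for qualitative data, and a standardised percentage is a reporting preference.

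**Conclusion.** The point holds as a worthwhile prespecification for a secondary endpoint. The plan names no covariate for the CRC model, its baseline rule cannot be applied literally, and the obvious covariate is already recorded before surgery. As written, the analysis is valid but exposed to chance depth imbalance and somewhat less precise than it need be.

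The textual gap is certain. The size is illustrative: it depends on the assumed depth SD, the borrowed ICC, the assumed CRC rates and the assumed slopes. Within those ranges the average power gain is 0 to about 8 points. The stronger argument is stability: adjustment removes nearly all of the dependence on an imbalance whose SD is about a quarter of a millimetre. The primary analysis is not affected.

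**What to change.** In the Data analysis section, extend the CRC sentence so that the two-level logistic model has treatment and the baseline Rec depth of the same tooth as fixed effects, with a random intercept for patient. Stating this in advance also prevents a choice between adjusted and unadjusted results once the data are seen.

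The cost is one sentence and no new measurement. The downsides are one more parameter in a sparse model (about 70 teeth, perhaps 25 of them uncovered) and an odds ratio conditional on depth as well as patient, usually further from 1 than the unadjusted one. Reporting model-standardised CRC percentages per arm, and their difference with a 95% confidence interval, would ease interpretation but is optional.

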The use of XCM in the treatment of gingival recessions has shown promising results and considered to be a suitable substitute to the connective tissue graft (Sanz et al. 2009, Herford et al. 2010, Schmitt et al. 2013). A recent systematic review (Atieh et al. 2016) was aimed to evaluate the use of XCM in comparison with CTG, CAF and FFG for the treatment of gingival recessions and/or insufficient KT in terms of clinical parameters and patient- related outcomes. The conclusions based on the only 2 available studies at unclear risk of bias (Cardaropoli et al. 2014, Jepsen et al. 2013) showed that no evidence resulted to demonstrate the effectiveness of XCM in achieving greater root coverage, recession reduction and gain in KT compared to CTG plus CAF. Superior short-term results in treating root coverage compared with CAF alone were possible. In addition, there was limited evidence that XCM may improve aesthetic satisfaction, reduce postoperative morbidity and shorten the operating time.

Therefore, the aim of the present CONSORT-based randomized clinical trial is to test the adjunctive benefit of XCM to the CAF in terms of root coverage, KT augmentation and patient-reported outcomes.

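### The t-tests for patient-reported outcomes leave out baseline scores that the trial already collects; ANCOVA on the repeated items would use them at almost no cost

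*Combined protocol and SAP*

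**What the plan says.** In Data analysis, quantitative variables get mixed models with treatment as a fixed effect and patient as a random effect, followed by "Baseline value will be used as a covariate". Questionnaire data are handled in a later, separate sentence: "For the patient-reported outcomes and experience measures t-tests will be applied". That sentence mentions no covariate and does not define the score to be tested.

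Under Patient Reported Outcomes, a pre-surgical questionnaire covers "problems with aesthetics, discomfort while brushing teeth, and hypersensitivity (whereas zero is no problem and 10 is major problems"). The questionnaires at 6 and 12 months cover "discomfort, chewing function, tooth cleaning procedures, dental hypersensitivity and esthetic outcome"; their response scale is not given. A diary covers the first 7 days after surgery.

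The Introduction sets out to test the benefit of the matrix "in terms of root coverage, KT augmentation and patient-reported outcomes". The only patient-reported entry among the secondary endpoints in Outcomes is "Patients satisfaction".

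**The concern.** The plan collects baseline patient-reported scores and names no use for them in the treatment comparison, although it adjusts its clinical measurements for baseline. The covariate sentence cannot safely be read as covering the questionnaires: they have their own sentence and their own test, and a patient random effect has no role when there is one score per patient and visit.

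Two things are at stake, both in secondary outcomes.

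- **Precision.** In a trial of 24 patients, a baseline score that predicts the follow-up score removes noise that the study can ill afford.
- **Pre-specification.** A t-test could be run on follow-up scores or on change scores. When the arms differ at baseline by chance, these two estimates move in opposite directions, so a choice made after seeing the data could alter the reported result.

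**Working it through.** **Inputs from the documents.** 12 patients per arm (Randomization and Allocation Concealment: "the 24 patients will be divided in 12 patients per treatment"), a two-sided 5% level, and the Sample Size line "Anticipation of 10% of patient drop-out". No power or sample size is stated for the patient-reported outcomes.

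**Assumptions.** The baseline-to-follow-up correlation r is not in the documents; 0.3, 0.5 and 0.7 are used, with r = 0 as the worst case. Scores are taken as normal with equal SD at both times, and the effect is 1 SD, for illustration.

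**The plan's own figure.** For the primary endpoint, 2 × (0.93 × (1.960 + 1.282) / 1)² = 18.18 teeth per arm. The design effect is 1 + (2.92 − 1) × 0.35 = 1.672. Patients per arm: 18.18 × 1.672 / 2.92 = 10.41, and 10.41 / 0.9 = 11.6, which rounds up to 12. The stated 12 per arm reproduces, and nothing below changes it.

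**Chance imbalance.** The SE of the baseline mean difference is √(2/12) = 0.408 SD. P(|difference| > 0.5 SD) = 2(1 − Φ(0.5/0.408)) = 0.22. Given a 0.5 SD imbalance, the follow-up-score estimate shifts by 0.5r and the change-score estimate by 0.5(r − 1):

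| r | Follow-up score | Change score |
|---|---|---|
| 0.3 | +0.15 SD | −0.35 SD |
| 0.5 | +0.25 SD | −0.25 SD |
| 0.7 | +0.35 SD | −0.15 SD |

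**Power for a 1 SD effect, 12 per arm.**

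- Follow-up t-test: 22 df, noncentrality 1/0.408 = 2.449, whatever the value of r.
- Change-score t-test: 22 df, SD = √(2(1 − r)) = 1.18, 1.00 and 0.77 at r = 0.3, 0.5 and 0.7.
- ANCOVA: 21 df, variance (1 − r²)(2/12 + D²/Sxx), averaged over the baseline mean difference D ~ N(0, 1/6) and the within-arm baseline sum of squares Sxx ~ χ² on 22 df. On average this is the t-test variance times (1 − r²)(1 + 1/20).

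| r | Follow-up t-test | Change-score t-test | ANCOVA | ANCOVA variance ÷ follow-up t-test variance | ANCOVA 95% CI half-width |
|---|---|---|---|---|---|
| 0 | 65% | 38% | 63% | 1.05 | 0.87 SD |
| 0.3 | 65% | 51% | 67% | 0.96 | 0.83 SD |
| 0.5 | 65% | 65% | 75% | 0.79 | 0.75 SD |
| 0.7 | 65% | 86% | 89% | 0.54 | 0.62 SD |

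The half-width for the follow-up t-test is 0.85 SD. ANCOVA overtakes that test at r of about 0.22 and has more power than the change-score test at every r shown. The two t-tests differ from each other by 14 points at r = 0.3 (65 − 51) and 21 points at r = 0.7 (86 − 65), and not at all at r = 0.5.

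**After drop-out.** 12 × 0.9 = 10.8, so about 11 per arm. The follow-up t-test then has 61%; ANCOVA has 62%, 71% and 86% at r = 0.3, 0.5 and 0.7, and the break-even r is about 0.23.

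**Check by simulation.** With 40,000 runs per value of r, and an effect of 1.20 SD at which the follow-up t-test has 80% power, ANCOVA reached 88% at r = 0.5. Type I error was 4.8% to 5.0% for ANCOVA and 4.9% to 5.0% for the t-test.

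**The case against.** The strongest reply is that nothing here is wrong, only less efficient. A t-test is unbiased under randomisation, and a single simple test for a mixed set of questionnaire items, many without a baseline, is defensible. That is true, and it limits the point to precision and pre-specification.

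The reach is also narrow. Only hypersensitivity is clearly asked at both times. Aesthetics and brushing discomfort may or may not be repeated in the same form, and satisfaction, the one listed patient-reported endpoint, has no described baseline. This stands too, so the change should not be presented as repairing the whole patient-reported aim.

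The gain rests on an unknown r and a large effect. With a 0.5 SD effect the follow-up t-test has 22% power and ANCOVA 22%, 26% and 36% at r = 0.3, 0.5 and 0.7. Surgery that removes the recession could weaken the correlation, and scores piling up at zero would weaken the linear relation. These points bound the benefit but do not reverse it: the worst case is about 2 power points.

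Finally, the imbalance shift is already contained in the t-test's standard error, and 0.15 to 0.35 SD lies well inside a half-width of 0.85 SD. This is correct: the shift illustrates the efficiency loss and is not a second harm. The open choice between follow-up and change score could be closed by one clarifying line without ANCOVA. That would settle the ambiguity but give up the precision.

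**Conclusion.** The concern holds. For patient-reported items asked on the same scale before and after surgery, the planned t-test names no baseline term and leaves the tested score undefined. At 12 per arm and a 1 SD effect, ANCOVA adds about 2, 10 or 24 power points over a follow-up-score t-test at r = 0.3, 0.5 or 0.7. It costs about 2 points if baseline is uninformative. The size depends on assumed correlations, an illustrative effect and roughly normal scores; the gap in the wording does not. It is worth correcting, but it affects secondary outcomes only.

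**What to change.** Amend the patient-reported sentence in Data analysis as follows.

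- For each 6- and 12-month item that repeats a baseline question on the same scale, use ANCOVA at each visit: follow-up score on treatment and baseline score, one value per patient.
- State the follow-up response scale and list the qualifying items before analysis: hypersensitivity if its scale matches, aesthetics and brushing discomfort only if both wording and scale match.
- Keep two-sample t-tests for satisfaction, chewing function and the 7-day diary.

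The cost is wording and one degree of freedom (22 to 21). The baseline questionnaire is already planned, so no extra patients, visits or data are needed. If r turns out to be zero, the 95% CI half-width is 0.87 instead of 0.85 SD.

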### *Surgical Procedure*

A single operator (RR) with more than 20 years of experience in mucogingival surgery will perform all surgical interventions. According to Zucchelli & De Sanctis (2000), an envelope split-full-split thickness flap without vertical incisions will be carried out. The horizontal incision will extend to include one tooth on each side of the teeth to be treated, in order to facilitate the planned coronal

repositioning of the flap tissue over the exposed root surfaces. The chronometer will start at the first incision. The oblique interdental incisions will be carried out keeping the blade parallel to the long axis of the teeth in order to dissect split-thickness the surgical papillae. Gingival tissue apical to the root exposures will be raised full-thickness in order to provide with more thickness that portion of the flap critical for root coverage. The most apical portion of the flap will be elevated split-thickness to facilitate its coronal displacement. Afterwards, the interdental papillae were de-epithelialized using a microscissor. The root surfaces will be mechanically treated with the use of curettes, avoiding the connective attachment area near the bone crest. A sharp dissection into the vestibular lining mucosa will be then carried out to eliminate muscle tension. Only at this point of the surgical procedure the envelope will be opened to allocate the patient to the treatment. In the test site the xenogenic collagen matrix (XCM)\* will be applied to all teeth with recession defect. The surgical technique employed in the test group consisted of the following additional steps:

1. After the preparation of the flap, the XCM will be cut into the right dimensions, measured with the probe, and its measurements recorded.
2. XCM will be placed from the CEJ to the bone crest on the recipient bed using single sutures, 7/0 PGA sutures.
3. The matrix will be rehydrated with blood, in order to reconstitute and maintain the maximal thickness possible.
4. The flap will be closed slightly coronal to the CEJ with a sling suture using resorbable PGA 6/0 sutures and avoiding any compression of the matrix.

In the control group, sling sutures will be performed to accomplish a precise adaptation of the buccal flap on the exposed root surfaces and to stabilize every single surgical papilla over the de-epithelialized anatomic papillae.

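### With 24 patients, must the plan name the estimator and small-sample reference for its mixed model?

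*Combined protocol and SAP*

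**What the plan says.** The Data analysis section specifies, for quantitative variables, a mixed model with treatment "as a fixed explicative variable and patient as a random variable", adjusted for the baseline value. On inference it says only "Estimates for the treatment effect, standard errors, p-values and 95% confidence intervals are provided", and it names MLwiN 2.21 without an estimation setting. The t-tests it mentions are for patient-reported outcomes.

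The unit of allocation is the patient. Under Surgical Procedure, "the envelope will be opened to allocate the patient to the treatment". Under Randomization and Allocation Concealment, "For designation of the treatment to each patient, the center will receive 24 sequentially numbered and sealed envelopes", and "the 24 patients will be divided in 12 patients per treatment". The opening sentence of that section speaks of randomising recession sites. That is loose wording: the envelopes, and the cluster formula under Sample Size, fit only patient-level allocation.

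Sample Size sets a "two- side 5% significance level, a power of 90" percent and uses "an intraclass correlation coefficient of 0.35". No section names an estimator, a reference distribution, degrees of freedom or a small-sample correction for the mixed model.

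**The concern.** Treatment differs only between patients, so measuring about three teeth in each does not add degrees of freedom for the treatment comparison: there are roughly 24 - 2 = 22. At that number two technical choices matter. ML estimates the between-patient variance with a downward bias, so its standard error is too small. A normal reference uses 1.96 where a t on 22 df needs 2.07. Both errors make the test too liberal and the interval too narrow.

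If the plan allowed these choices to be settled after the data were seen, a borderline primary result could be moved across 5%. The 95% interval for recession reduction could also cover as little as about 92% of the time.

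**Working it through.** **Inputs from Sample Size:** difference 1 mm, SD 0.93 mm, 2.92 teeth per patient, intraclass correlation (ICC) 0.35, two-sided alpha 0.05, power 90%, drop-out 10%.

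**The plan's own figure first.**
- Teeth per arm if independent: 2 × [0.93 × (1.960 + 1.2816)]² = 18.18.
- Design effect: 1 + (2.92 - 1) × 0.35 = 1.672.
- Patients per arm: 18.18 × 1.672 / 2.92 = 10.41; with drop-out, 10.41 / 0.90 = 11.56, rounded up to 12.

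The stated 12 per arm is reproduced and is not in question.

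**Balanced benchmark for test size.** With K patients and df = K - 2:
- REML with z has size P(|t_df| > 1.96).
- ML shrinks the standard error by √(df/K), so ML with z has size P(|t_df| > 1.96 × √(df/K)).

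| Patients | df | REML + z | ML + z |
|---|---|---|---|
| 24 | 22 | 6.3% | 7.4% |
| 22 (about 10% drop-out) | 20 | 6.4% | 7.6% |

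**Simulation under no treatment effect.** Random-intercept model, treatment plus tooth-level baseline, SD 0.93, one time point, no interaction, 24 or 22 patients. Two sets of runs were made, with 20,000 and 12,000 trials per setting. Assumptions that the documents do not supply: teeth per patient ranging over 2-3, 2-5 or 2-6 (mean about 2.92), baseline ICC 0.35, baseline slope 0.5 or 0.3. Rejection rates over both sets (ICC 0 in the second set only):

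| ICC | ML + z | REML + z | REML + t, K - 2 df |
|---|---|---|---|
| 0.35 (plan) | 7.3-8.2% | 5.9-6.6% | 4.7-5.2% |
| 0.50 (assumed) | 7.6-7.9% | 6.3-6.7% | 4.8-5.1% |
| 0.20 (assumed) | 7.3-7.8% | 6.0-6.3% | 4.7-5.1% |
| 0.10 (assumed) | 6.5-7.0% | 5.4-5.9% | 4.2-4.5% |
| 0 (assumed) | 5.5% | 4.5-4.7% | 3.5-3.7% |

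At ICC 0.35 interval coverage is 91.8-92.7%, 93.4-94.1% and 94.8-95.3% in the same order. Near ICC 0 the estimated patient variance is often cut off at zero, which removes most of the inflation and makes the t rule conservative.

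**What the reference changes in practice.** The critical values are 2.074 (22 df) and 2.086 (20 df).
- Interval width, REML + t over REML + z: 2.074/1.960 = 1.058; 2.086/1.960 = 1.064.
- A z-based p-value loses significance under t on 22 df only if it lies between 2 × [1 - Φ(2.074)] = 0.038 and 0.05.
- Power at 1 mm with all 24 patients: standard error √[2 × 0.93² × 1.672 / (12 × 2.92)] = 0.287, non-centrality 1/0.287 = 3.48, giving 93% with z and 91% with t on 22 df.

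**The case for a change.** The strongest case for acting is that the omission is real, the cost of filling it is one sentence with no extra patients, and the trial is small enough for the choice to show. Under the plan as written, the same data could be analysed at a true level near 5%, 6.3% or 8%, and naming the software does not settle which. Both elements matter: at ICC 0.35, ML with the t reference still runs at 6.3-6.5%.

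All of that arithmetic stands. What it does not establish is a fault in a stated rule. Every inflated figure needs an analyst decision that appears nowhere in the documents, and the 7-8% figures need two such decisions together. The planning ICC of 0.35 comes from one earlier study and is not described as baseline-adjusted, whereas the model adjusts for baseline. A lower adjusted ICC would shrink the inflation. Patients minus 2 is also only one defensible reference; Satterthwaite or Kenward-Roger would serve. Nor would fixing this detail alone guarantee 5%: the primary endpoint is named at both 6 and 12 months, and interaction terms enter only if significant. The simulations include neither feature.

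**Conclusion.** The concern does not call for a change. The plan gets the consequential decision right: patient is a random effect, so teeth are not treated as independent. What is missing is a fitting and reference convention that a competent analyst of a 24-patient clustered trial supplies as routine, and the plan permits the sound choice. REML with a t on patients minus 2 holds 4.7-5.2% at the planning ICC. A t-based interval can be computed by hand from a REML estimate and standard error, whatever the software prints.

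If an analyst did use Wald z, the excess would be about 1 point with REML and 2-3 points with ML at ICC 0.35. It would be smaller at 0.10 and mostly gone at zero. These sizes rest on the assumed spread of teeth and baseline behaviour, a single time point and recession reduction only. They say nothing about other endpoints or the logistic model for complete root coverage. A reader of the results should check which estimator and reference were used if the primary p-value falls between about 0.04 and 0.05.
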